wrist), and baseline Corneometer® measurements will be taken. Per the Randomization Schedule. each participant will be assigned to either Marathon® or Cavilon™ (designated SBP). The designated SBP will be applied to the volar forearm and inner elbow "test areas" on the participants' dominant arm (as determined by the participant). The other SBP will be applied to the volar forearm and inner elbow "test areas" on the participants' non-dominant arm. A distinct area of each volar forearm of the participants will be used as an "untreated control area" for the test areas on that forearm. To assess baseline skin hydration, study personnel will use the Corneometer® to take the average of five initial measurements of skin capacitance and the standard deviation of the measurements, for each of the untreated control areas and the volar forearm and inner elbow test areas. After the baseline measurements have been recorded, the study personnel will apply the two SBPs, Marathon® and Cavilon™, according to the Randomization Schedule to test areas on the participants' volar forearm and the inner elbow. After the SBPs have been left to dry for at least one minute or have dried completely, Corneometer® measurements will be repeated in the untreated control areas and the volar forearm and inner elbow test areas in a manner similar to the baseline measurements. Thereafter, daily Corneometer® measurements will be taken over a seven-day period with a two-day break over the weekend. During the study period, participants will be allowed to bathe their arms using a standardized soap provided by the study personnel but will be instructed to minimize scrubbing or any other abrasion of the skin of the volar forearms and inner elbows. In addition, participants will be instructed not to engage in activities, for eg, sports (eg, tennis) or holding a baby that may cause significant abrasion on one arm and not the other. On the last day of the study (Visit 6), study personnel will take the last set of Corneometer® measurements. In addition, participants will complete surveys regarding their experience with the two SBPs on specific days during study participation.

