# 6.2.2 Randomization of Target Areas

Study personnel will confirm that the washout period of minimum 18 hours prior to Visit 1, has been successfully completed. Participants will wash their forearms and inner elbows with a standardized soap and use paper towels to dry each arm. After the participants' forearms and inner elbows are fully dried, they will be randomized according to the Randomization Schedule.

Figure 6.2.2. Randomization of Untreated Control Areas and Test Areas on the Volar Forearms and Inner Elbows

[figure not shown]

Figure 6.2.2. Key	
LL	Lower left
UL	Upper Left
LR	Lower Right
UR	Upper Right
LIE	Left Inner Elbow
RIE	Right Inner Elbow

Note: The inner elbow test areas will receive the same SBP as the one applied to the test area of the same arm

Medline Industries, LP

An evaluation of the skin protection characteristics of two commercially available skin barrier protectants MED-2022-DIV71-003

08-AUG-2022

Version 2.0 CONFIDENTIAL Page 17 of 28

Randomization will assign each participant to either Marathon® or Cavilon™ (designated SBP). The designated SBP will be applied to the volar forearm and inner elbow "test areas" of the participant's dominant arm, as determined by the participant. The other SBP will be applied to the volar forearm and inner elbow "test areas" of the participant's non-dominant arm. The SBP applied to the volar forearm and inner elbow test areas of a particular arm will be the same. Randomization will provide an equal probability for an SBP to be assigned to either the dominant or non-dominant arm. A distinct area on a particular volar forearm of the participant will be used as an "untreated control area" for the test areas on the same forearm.

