#### 8. STATISTICAL CONSIDERATIONS

#### 8.1. Sample Size Determination

A sample size of 42 was elected for a superiority margin of at least 15 arbitrary capacitance units  $(A.C.U)^{10}$  as measured by the Corneometer® with an estimated mean of pair differences of 17.5 and the standard deviation of 5.05, given the 80% power at Bonferonni adjusted significance level of  $\alpha = .0125$ . Internal evaluation SBP data was used as a starting point, and PASS- Paired T-Tests for Superiority by a Margin procedure was utilized for the sample size estimation (PASS 2021 Power Analysis and Sample Size Software (2021). NCSS, LLC. Kaysville, Utah, USA, ncss.com/software/pass).

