# **Analysis of Primary Endpoints**

# 8.8.1. Primary Endpoints

Degradation of the SBP over seven days as measured by the Corneometer®.

The breakdown of the SBPs on the volar forearm test areas will reflect the duration of wear of the SBPs. Independent sample t-tests or non-parametric equivalent tests will be used to compare mean Marathon® and Cavilon™ Corneometer® values at baseline (Visit 1), Visit 2, Visit 3, Visit 4, Visit 5, and the final Visit 6 for untreated control area and volar forearm test area measurements. Paired-sample t-tests will be used to compare any two data points for a given SBP and location.

The breakdown of the SBP on the inner elbow test area, relative to the corresponding volar forearm test area, will reflect the durability of the products. Derived variables will be created to calculate the difference between the volar forearm test area measurement and the inner elbow test area measurement at baseline (Visit 1), Visit 2, Visit 3, Visit 4, Visit 5, and the final Visit 6. Independent sample t-tests or non-parametric equivalent tests will be used to compare mean Marathon® and Cavilon™ Corneometer® difference values at baseline (Visit 1), Visit 2, Visit 3 and the final Visit 6 on Day 8. Paired-sample t-tests will be used to compare any two data difference points for a given SBP.

Both degradation and durability endpoints will be graphed across time by SBP with and without 95% confidence intervals of the mean.

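### The untreated control readings never correct the test-area readings, and the between-product tests adjust for neither control nor baseline: precision is lost between products, and forearm within-product change is open to hydration drift

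*Combined protocol and SAP*

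**What the plan says.** All references are to the combined protocol and SAP.

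- **Role of the control.** Section 4.1 reserves an area of each forearm as the untreated control "for the test areas on that forearm". Section 6.2.2 repeats this: "for the test areas on the same forearm". Under 6.2.3, 6.3.1 and 6.4.1 the control square is read before application, after application and at Visits 2 to 6, with the same five-reading average as the test squares.
- **Between-product tests.** Section 8.8.1 compares mean Corneometer values of the two products at each visit by independent-sample t-tests or a non-parametric equivalent, "for untreated control area and volar forearm test area measurements". Control and test area are two separate outcomes. For endpoint 1b the outcome is forearm minus inner elbow.
- **Within-product tests.** "Paired-sample t-tests will be used to compare any two data points for a given SBP and location". A visit can therefore be compared with baseline, but location is held fixed, so this is not test area against control.
- **Derived variables and covariates.** Section 8.6 defines the degradation rate as (Co − Ct)/Co, with interest in when it reaches 50%. There is no control term, and the plan does not say whether Co is the pre- or post-application reading. Section 8.8 names age, sex and dominant arm as covariates, but neither control nor baseline.

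**The concern.** The Corneometer measures skin hydration, and section 4.1 takes a rising reading as film breakdown. Hydration can also move for other reasons over about a week that includes bathing and a weekend gap. The control square is the design's means of seeing such movement, yet no analysis brings it to bear on the treated squares.

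Two things are at stake. First, within a product, any general rise in hydration that reaches the treated forearm square is indistinguishable from film wear, both in the visit-to-visit tests and in the time to 50% degradation. Second, between products, arm-to-arm differences in hydration that the trial has measured stay in the error term.

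**Working it through.** **1. Reproduce the plan's sample size.** Inputs from section 8.1: n = 42, margin 15, mean pair difference 17.5, SD 5.05, α = .0125 ("with an estimated mean of pair differences of 17.5 and the standard deviation of 5.05"; "given the 80% power at Bonferonni adjusted significance level of" .0125). Sidedness is not stated; one-sided reproduces the figure.

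Excess over margin = 17.5 − 15 = 2.5. Noncentrality = 2.5/5.05 × √42 = 3.21, df = 41. Noncentral-t power = 80.7%, and 42 is the smallest n reaching 80%.

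**2. Effect of drift on each comparison.** Let a shift d reach both treated squares of a participant.

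- Product difference: (M + d) − (C + d) = M − C, so d cancels.
- Within-product forearm change: (M₁ + d) − M₀, so d stays.
- Endpoint 1b, forearm minus elbow: drift common to both sites cancels.

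A simulation with n = 42, a drift of 5 A.C.U., no film loss and assumed variances agrees. The mean product difference was 0.01 A.C.U. and the paired product test rejected in about 5% of trials, while the within-product paired test rejected in over 99%.

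**3. Size within product.** Assume the SD of change over time equals the planning SD of 5.05; the documents do not give it. The smallest observed mean shift significant at the .05 level of section 8.8 is t(.975, 41) × 5.05/√42 = 2.02 × 0.779 = 1.57 A.C.U.

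For the degradation rate, take Co as a post-application reading with assumed values and no film loss:

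- Co = 20, rise of 10: (20 − 30)/20 = −50%.
- Co = 20, rise of 5: (20 − 25)/20 = −25%.
- Co = 10, rise of 5: (10 − 15)/10 = −50%.

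Drift alone can therefore reach 50% in magnitude.

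**4. Precision between products.** Start from the paired margin test of section 8.1. Let R be the multiple correlation of the outcome pair difference with the control and baseline pair differences. Adjusted SD = 5.05 × √(1 − R²), with df = 42 − 3 = 39.

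| R (assumed) | Adjusted SD | SE reduction | Power at n = 42 |
|---|---|---|---|
| unadjusted, df 41 | 5.05 | – | 80.7% |
| 0 | 5.05 | 0% | 80.6% |
| .3 | 4.82 | 5% | 84.4% |
| .5 | 4.37 | 13% | 91.0% |
| .7 | 3.61 | 29% | 98.2% |

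Plain subtraction of a single reference of equal variance multiplies the SD by √(2(1 − r)), where r is its correlation with the outcome. That gives power of 48.3% at r = 0, 65.1% at .3, 80.7% at .5 and 96.2% at .7. Subtraction gains only when r exceeds .5, so covariates are the safer form for this comparison.

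**5. Why a covariate does not serve within product.** With a centred control covariate, the intercept is still the raw mean change, so mean drift is untouched. In simulation (drift 5, no film loss, assumed variances) it rejected in about 100% of trials. An uncentred covariate rejected in 14% to 94%, depending on the variances, because noise in the control reading attenuates the slope. Subtracting the control change gave 5% when film-covered skin followed the drift fully. When it followed by half, the residual is 0.5 × 5 − 5 = −2.5 A.C.U., and the test rejected in about 96%.

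**The case against.** The strongest reply is that the primary aim includes comparing the products, and that comparison is protected: both products are on every participant, with assignment to the dominant arm randomised. This stands. A reader might infer from the unused control that drift biases the product comparison; the design does not support that for shared drift. Arm-specific drift adds noise.

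A reader might also infer that baseline is never used. That is not so: the within-product paired tests can take baseline as one of the two points, and the degradation rate scales to an original reading, though an undefined one. If the control square counts as a location, its own change over time is tested too. Drift would then be shown beside the test areas, but not removed from them. Nor does the drift problem extend to movement common to both sites in endpoint 1b.

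On size, R has no source in the documents and the gain could be nil. The 1.57 A.C.U. limit borrows an SD meant for product differences and is about a tenth of the plan's 15 A.C.U. margin (1.57/15 = 0.10). Both are fair cautions. But the margin belongs to the product comparison, whereas the within-product tests and the 50% threshold carry no margin.

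Finally, the 80.7% belongs to a paired test, while 8.8.1 names independent-sample tests. That mismatch is a separate matter; the gains above assume a within-participant comparison.

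**Conclusion.** The point holds in a limited form. A control built into the design, and read at every visit, corrects nothing, and the between-product tests adjust for neither control nor pre-application baseline.

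- **Between products:** a loss of precision, not bias from shared drift. The size depends wholly on R, and the worst case from adjusting is about 0.1 point of power.
- **Within product, forearm only:** change between visits and time to 50% degradation cannot separate drift from film loss, to the extent that drift reaches film-covered skin. The documents do not say how large drift is or how far film-covered skin follows it, so the size of the error is unknown. The 1.57 A.C.U. figure shows only how small a shift would be declared significant under the assumed SD.

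This should be changed before analysis. It does not undermine the randomised contrast.

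**What to change.** In section 8.8.1:

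1. In the within-participant product comparison at each visit, enter two covariates, each as a Marathon-minus-Cavilon difference: the same-visit control reading, and the pre-application baseline of the outcome. For endpoint 1b that baseline is the forearm-minus-elbow difference. The elbow has no control square, so the same-arm forearm control serves.
2. For forearm within-product change, report beside the raw change the control-referenced change: change in the test square minus change in the same-arm control square. Do not use covariate adjustment here, since it does not remove mean drift. State as a limitation that subtraction over-corrects if film-covered skin follows bare-skin drift only in part.
3. Keep the product comparison on the control area as a descriptive check only.

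The cost is SAP wording and two degrees of freedom. All the readings are already scheduled.

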#### 3. OBJECTIVES AND ENDPOINTS

OBJECTIVES	ENDPOINTS	JUSTIFICATION FOR ENDPOINTS
Primary		
To evaluate and compare the duration of wear and durability of Marathon® and Cavilon™	Degradation of the SBPs over seven days as measured by the Corneometer.  1a. The breakdown of the SBPs on the volar forearm will reflect the duration of wear of the SBPs.  1b. The breakdown of the SBPs on the inner elbow, relative to the volar forearm, will reflect the durability of the SBPs.	This endpoint will be an objective measurement of the deterioration of the SBPs, and in turn, the skin protection they offer over time.
Secondary		
To collect information on the participant experience with the two SBPs	Responses to participant surveys	This endpoint evaluates the participants' experience with the SBPs.

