# 6.2.3 Application of Skin Barrier Protectants (SBPs) and Corneometer® Measurements

Study personnel will draw 2-inch x 2-inch squares on the participants' forearms for each untreated control area and each test area using a non-toxic marker, such that three squares are marked on each volar forearm and inner elbow taken together. The lower squares on the volar forearms (LL and LR) will be marked about two inches above each wrist and will be used as untreated control areas. The upper squares on the volar forearms (UL and UR) will be used as test areas. The squares marked on the inner elbows of the participants (LIE and RIE) will be used as test areas as well. Refer to Figure 6.2.2 for details.

To measure baseline skin hydration, study personnel will use the Corneometer® to take the average of five measurements of skin capacitance and the standard deviation of the measurements for both the left and right forearm within each of the untreated control areas and volar forearm and inner elbow test areas. The Corneometer® measurements will be recorded in the CRF.

After the baseline measurements have been taken, study personnel will apply a thin layer of either Marathon ® or Cavilon TM (per the Randomization Schedule), such that the SBP covers the participants' skin within the border of the volar forearm and inner elbow test area squares. Each volar forearm will also include a 2-inch x 2-inch untreated control area square where no SBP will be applied. The participants will not be informed about the type of SBP applied to the volar forearm and inner elbow test areas. The participants will be instructed not to leave the study room, and that their forearms must remain exposed such that no article of clothing comes in contact with their forearms and inner elbows.

After the SBPs have been left to dry for at least one minute or have dried fully, Corneometer® measurements will be repeated in a manner similar to the baseline measurements, for each of the two untreated control areas and four test areas. The average of the Corneometer® measurements and the standard deviation of the measurements will be recorded in the CRF.

Participants will be dismissed from the study room and will be instructed to return the next day (within a  $24 \pm 4$  hours window) for Visit 2.

Medline Industries, LP
An evaluation of the skin protection characteristics of two commercially available skin barrier protectants
MED-2022-DIV71-003
08-AUG-2022

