### 8.8. Statistical Analysis

Statistical analyses will be conducted in SAS® software, Version 9.4 or higher of the SAS System for Windows (Copyright © 2013 SAS Institute Inc.) or other appropriate statistical software. P < .05 will be considered statistically significant.

All continuous variables will be summarized for the full sample and by SBP group using the following descriptive statistics: (non-missing sample size), mean, standard deviation, median, maximum and minimum. The frequency and percentages (based on the non-missing sample size)

Medline Industries, LP
An evaluation of the skin protection characteristics of two commercially available skin barrier protectants
MED-2022-DIV71-003
08-AUG-2022

Version 2.0 CONFIDENTIAL Page 23 of 28

of observed levels will be reported for all categorical measures. 95% confidence intervals will be calculated for all means.

Spearman correlation analysis will be used to examine possible associations between the key variables of Marathon® or Cavilon™ use and the Corneometer® measurements at various timepoints with covariates of age, sex, and dominant arm. Additional t-tests or non-parametric tests will be employed to further examine any significant associations found in the correlational analyses between key and covariate measures.

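### Section 8.8.1 puts an open family of unadjusted within-product tests under the primary endpoint, but names no between-product test of change over time

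*Combined protocol and SAP*

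**What the plan says.** The primary objective in section 3 is comparative: "To evaluate and compare the duration of wear and durability of Marathon® and Cavilon™". The endpoint is degradation of the products over seven days by Corneometer.

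Section 8.8.1 plans two kinds of test for it.

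- **Between products.** On the control squares and the treated forearm squares, independent-sample t-tests, or non-parametric equivalents, compare the two products "at baseline (Visit 1), Visit 2, Visit 3, Visit 4, Visit 5, and the final Visit 6". The forearm-minus-elbow difference is compared in the same way at Visits 1, 2, 3 and 6.
- **Within product.** "Paired-sample t-tests will be used to compare any two data points for a given SBP and location". For the derived difference: "Paired-sample t-tests will be used to compare any two data difference points for a given SBP".

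The within-product sentences name no visit pairs and no order, and do not call the tests descriptive. Section 8.8 sets one threshold for everything: "P < .05 will be considered statistically significant". The only multiplicity adjustment is in section 8.1, where the sample size uses a "Bonferonni adjusted significance level of" .0125. That level is not tied to any test in section 8.8.

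**The concern.** There are two linked gaps.

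First, the set of within-product tests is open. Any two visits may be compared for each product and series, each at .05, under the heading reserved for the primary endpoint.

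Second, the endpoint describes change over time, yet the plan tests change only within each product. The between-product tests compare levels at single visits. Section 8.6 defines a per-participant degradation rate with a 50% mark, but section 8.8.1 assigns it no test.

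Together these leave room for a familiar misreading: one product's readings rose significantly between two visits, the other's did not, so the products differ in wear. That pattern is not a test of one product against the other, and it arises often when they behave alike. With the visit pair free to be chosen after the data are seen, a primary-endpoint statement about comparative wear could rest on it. Correcting only the between-product tests for multiplicity would not touch this route.

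**Working it through.** **The plan's own figure.** Section 8.1 gives a margin of 15, mean pair difference 17.5, SD 5.05, 80% power and alpha .0125. The effect beyond the margin is 17.5 − 15 = 2.5. A paired t-test (noncentral t, one-sided .0125) needs n = 42, with power 80.7%, so the stated N reproduces. Two-sided .0125 would need 49. The level is .05/4 = .0125, but the four tests are not named. The N is not in dispute. It was sized for a paired between-product test, which section 8.8.1 does not list.

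**Counting the within-product tests.** The six listed time points give C(6,2) = 15 pairs per series.

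| Series counted | 6 time points | 7 time points |
|---|---|---|
| Forearm only | 15 × 2 products × 1 = 30 | 42 |
| Forearm + difference | 15 × 2 × 2 = 60 | 84 |
| Control + forearm + difference | 15 × 2 × 3 = 90 | 126 |
| Adding the elbow itself | 15 × 2 × 4 = 120 | 168 |

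The third row follows the locations that section 8.8.1 names. The elbow row and the seventh time point are possible because section 6.2.3 repeats the measurements after application at Visit 1, "for each of the two untreated control areas and four test areas"; C(7,2) = 21.

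**One significant, the other not, when wear is identical.** Take one visit pair, the same true change in both products, power p in each within-product test, and correlation r between the two arms' test statistics (bivariate normal approximation). Then P(discordant) = 2 × [p − P(both significant)]. The documents give neither p nor r, so both are assumed.

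- p = .50, r = .5: P(both) = .3333, so 2 × (.50 − .3333) = 33%. Over r = 0 to .7: 50% down to 25%.
- p = .80, r = .5: P(both) = .6872, so 2 × (.80 − .6872) = 23%. Over r = 0 to .7: 32% down to 17%.
- p = .90, r = .5: 13.5%.
- p = .95, r = .5: 7.6%.
- p = .99, r = .5: 1.7%.

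A direct test of the difference in change at .05 would be wrong 5% of the time.

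**Free choice among the 15 forearm pairs.** This was simulated with 3,000 trials per setting, n = 42, two-sided .05 and identical true courses. Assumptions: SD of a within-product change 5.05 (borrowed from section 8.1, where it describes pair differences), errors independent across visits, a linear rise, and between-arm correlation 0, .5 or .8. At least one discordant pair appeared in:

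- 49–60% of trials with no change;
- 64–99.5% for a total rise of 2.5 to 10 units;
- 5–7% for a total rise of 17.5 units.

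One pre-named between-product contrast of change was wrong in 4–6% of trials in every scenario.

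**If nothing changes anywhere.** One 15-pair series gives at least one false positive in about 37–38% of trials. The 90-test family does so in about 94–95%, 85–89% and 72% at between-series correlation 0, .5 and .8; the spread is variation between simulation runs. These are upper illustrations, because they require flat readings in every series.

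**The case against.** The case on the other side is substantial, and much of it stands.

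- **The plan has direct product comparisons and never says it will use within-product results in their place.** This is correct. A reader might infer that the sponsor intends to claim a product difference from within-product P values, but no sentence says so. What stands is that no sentence rules it out, and that the direct tests compare levels at single visits, not change.
- **The objective is to evaluate as well as to compare, so within-product change is a legitimate output.** Agreed. That supports describing it, and does not require an unrestricted set of significance tests under the primary endpoint.
- **Readings on treated skin are expected to rise as the product breaks down (synopsis and section 4.1 note).** A significant rise there is mostly a true finding. A reader might take the 72–95% figure as this trial's false-positive rate. The documents do not support that, because the figure needs no change in any series. Untreated control is where flat readings are most natural, and a false positive there is not a wear claim.
- **Discordance shrinks as wear grows.** Also right: it is below 2% at 99% power, and 5–7% over the whole forearm series for a 17.5-unit rise.
- **A 95% confidence interval carries the same information as the paired test, and new contrasts need an alpha.** Both are fair. Four independent tests at .05 would give 1 − .95⁴ = 18.5% familywise. The replacement wording therefore has to bar the same inference from intervals and has to set the level.

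**Conclusion.** The concern holds in a limited form. Section 8.8.1 gives primary-endpoint standing to an unspecified, unadjusted family of within-product tests, and the plan lacks a between-product test of change over an interval. The text alone establishes both gaps. The count of about 90 is one reading within 30 to 168.

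The size of the risk is conditional. With identical wear, a given visit pair is discordant in about 33% of trials at 50% power and 23% at 80%, falling to 13.5% at 90% and under 2% at 99%, with assumed between-arm correlation 0.5. It matters most if wear over the interval is small or moderate, and little if wear is large. Neither power nor correlation can be taken from the documents.

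The finding is that the plan leaves a misleading inference open. It does not show that the plan intends that inference, or that a false claim is near certain. The mismatch between .0125 in section 8.1 and .05 in section 8.8 for the between-product tests is a related but separate matter.

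**What to change.** Replace both within-product sentences in section 8.8.1 with:

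> Change over time within each SBP will be described by the mean change from the Visit 1 post-application reading with a 95% confidence interval. These are descriptive, and no difference between SBPs will be inferred from one SBP's change being significant, or its interval excluding zero, when the other's is not. Change is compared between SBPs by a paired test of the within-participant difference (Marathon arm minus Cavilon arm) in change from post-application to Visit 4 and to Visit 6, for the forearm and for the forearm-minus-elbow difference. These four contrasts are each tested at the Bonferroni level of .0125 already used in section 8.1, and the per-visit comparisons are supportive.

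Visit 4 closes the first 72 hours, which the section 4.1 note treats as the more important window, and Visit 6 is the last visit. Four tests at .0125 sum to .05 (1 − .9875⁴ = 4.9% if independent). The paired form matches the basis on which N = 42 was set. The sponsor should also state whether the tests are one- or two-sided, since 42 reproduces only one-sided.

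The cost is wording only, with no new data or visits. Within-product P values are no longer reported as primary results. The 80% power in section 8.1 belongs to its own margin and SD, so it should not be assumed for these contrasts without a check.

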# 1.2. Schedule of Activities (SOA)

Assessments and Activities#	Pre-visit Activities	Visit 1	Visit 2–5	Visit 6 (Final visit)
Informed consent	X			
Participant Screening	X			
Demographics	X			
Participants complete minimum 18 hours washout period	X			
Participants wash forearms and inner elbows with standardized soap, and dry them using paper towels		X		
Participant forearms and inner elbows allowed to dry		X		
Randomization of SBP to be applied to the dominant arm of the participant §¥		X		
Baseline Corneometer® measurements taken		X		
SBPs applied at the volar forearm and inner elbow test areas according to the Randomization Schedule§		X		
SBPs allowed to dry		X		
Post-application Corneometer® measurements taken at untreated control areas and test areas		X	X	X
Participants complete surveys regarding experience with the SBPs ¥		X	X	X
Monitoring for adverse device events		X	X	X
Participant dismissal				X

# Study activities will occur after informed consent has been signed, and the participant has met all the inclusion criteria and none of the exclusion criteria.

08-AUG-2022

Version 2.0 CONFIDENTIAL Page 10 of 28

§ Randomization will assign each participant to either Marathon® or Cavilon™ (designated SBP). The designated SBP will be applied to the volar forearm and inner elbow test areas of the participants' dominant arm (as determined by the participant), whereas the other SBP will be applied to the volar forearm and inner elbow test areas of the participants' non-dominant arm.

\*The same type of SBP will be applied to the volar forearm and inner elbow test areas.

<sup>£Participants will complete surveys on Visits 1, 3, and 6.

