#### 8.6. Derived Variables

The difference between volar forearm and inner elbow measurements will be calculated for each timepoint.

Degradation Rate will be calculated as =  $(C_o - C_t) / C_o$ , where  $C_o$  is the original Corneometer® measurement value and  $C_t$  is the Corneometer® measurement at a given follow-up timepoint. We will be looking to see when the degradation rate reaches 50%.

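### The plan gives 95% intervals for each product's own mean but none for the within-participant product difference on which the study was sized

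*Combined protocol and SAP*

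**What the plan says.** - **Design.** The schedule of activities (section 1.2) puts one product on the dominant arm; on the non-dominant arm, "the other SBP will be applied to the volar forearm and inner elbow test areas". Every participant is therefore a matched pair.
- **Sizing.** Section 8.1: "A sample size of 42 was elected for a superiority margin of at least 15 arbitrary capacitance units". It assumes a mean pair difference of 17.5 with SD 5.05, 80% power and a Bonferroni-adjusted alpha of .0125, using a paired superiority-by-a-margin procedure.
- **Derived variables.** Section 8.6 defines a forearm-elbow contrast within an arm ("The difference between volar forearm and inner elbow measurements will be calculated for each timepoint") and a degradation rate. It defines no contrast between the products.
- **Summaries.** Section 8.8: "All continuous variables will be summarized for the full sample and by SBP group using the following descriptive statistics", and "95% confidence intervals will be calculated for all means". The same section sets significance at P < .05.
- **Tests and graphs.** Section 8.8.1: "Independent sample t-tests or non-parametric equivalent tests will be used to compare mean Marathon® and Cavilon™ Corneometer® values at baseline" and the later visits. Paired tests are kept for contrasts within one product: "Paired-sample t-tests will be used to compare any two data points for a given SBP and location". For display: "Both degradation and durability endpoints will be graphed across time by SBP with and without 95% confidence intervals of the mean".

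**The concern.** The primary objective is comparative, and the sample size targets a difference within the person. As written, the report would contain two means per visit, an interval around each, and an unpaired P value. It would contain no estimate of the product difference with its uncertainty, and so nothing to set against 15 A.C.U.

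The by-product intervals cannot fill the gap. On the forearm, each includes person-to-person variation in skin hydration, part of which cancels when the two arms of one person are subtracted. A reader who compares the products by whether the bars overlap is using the wrong yardstick. Even clearly separated bars show at most that the means differ, not that they differ by more than the margin.

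**Working it through.** **Inputs.** From section 8.1: n = 42, mean pair difference 17.5, SD of pair differences 5.05, margin 15, alpha .0125, power 80%. The documents give neither the SD of a single product's readings nor the within-person correlation rho. Both are assumed over a range below, with equal SDs for the two products.

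**1. The plan's own figure.** Paired t-test, noncentral t, effect beyond the margin 17.5 - 15 = 2.5, SD 5.05. One-sided alpha .0125 gives n = 42 with power 80.7%, which matches. Two-sided .0125 would need 49. The design calculation is therefore paired and, by inference, one-sided; the plan does not state the sidedness.

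**2. Interval for the product difference.** The standard error is 5.05/√42 = 0.779.
- 95%: 2.0195 × 0.779 = 1.57, so 17.5 ± 1.57 = 15.93 to 19.07.
- 97.5% (two-sided counterpart of one-sided .0125, since 2 × .0125 = .025): 2.327 × 0.779 = 1.81, so 15.69 to 19.31.

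Both exclude 15. Neither depends on rho, because 5.05 is already the SD of the differences.

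**3. What the planned intervals would look like.** Single-product SD = 5.05/√(2(1 - rho)). Own-mean half-width = 2.0195 × SD/√42. Two bars stop overlapping when the means differ by twice that. Unpaired half-width for the difference = 1.989 × SD × √(2/42).

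| rho | SD per product | Own-mean half-width | Gap at which bars separate | Unpaired half-width | Paired half-width |
|---|---|---|---|---|---|
| 0 | 3.57 | 1.11 | 2.23 | 1.55 | 1.57 |
| 0.3 | 4.27 | 1.33 | 2.66 | 1.85 | 1.57 |
| 0.5 | 5.05 | 1.57 | 3.15 | 2.19 | 1.57 |
| 0.7 | 6.52 | 2.03 | 4.06 | 2.83 | 1.57 |
| 0.9 | 11.29 | 3.52 | 7.04 | 4.90 | 1.57 |

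The gap needed for separation is 1.4 to 4.5 times the paired half-width. Even an interval for the difference, if built from the unpaired test, could miss the design target: at 17.5 it is 15.31 to 19.69 for rho 0.5, but 14.67 to 20.33 for rho 0.7, which includes 15.

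**4. How often overlap would mislead.** Simulation of 20,000 trials of 42 pairs, SD of differences 5.05, assumed true difference 3. The paired 95% interval excludes 0 in about 96% of trials. Among those, the bars overlap in about 13% at rho 0 (SD 3.57), 53% at SD 5 and 99.9% at SD 10. At the planned difference of 17.5 they overlapped in none, at SD 10 or SD 15.

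**The case against.** A reader might infer that the graph misstates the comparison or that its bars are wrong. The documents do not support that. A 95% interval for one product's mean is valid for that mean, section 8.8.1 assigns the comparison to tests and not to the graph, and a version of the graph without intervals is already planned.

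Nor would overlapping bars generally hide a real difference. The overlap figures rest on an SD the plan does not give and on a true difference of 3, which is an assumption far below the planned 17.5. At 17.5 the bars separate clearly. Some of the conservatism of the overlap rule has nothing to do with pairing: the ratio is already 1.4 at rho 0. For durability, a person-level shift common to forearm and elbow has been subtracted before plotting, so less between-person variation may remain. All of this stands, and it limits the claim about the graph.

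It can also be said that the root problem is the unpaired test, and that once a paired test is used the promise of intervals for all means would cover the mean difference. The two changes do belong together. But that promise reaches only variables the plan defines, and section 8.6 defines no product difference. Changing the test alone would leave the tables and graphs as they are.

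Finally, a single line at +15 on Marathon minus Cavilon would be a poor remedy. Readings rise as a product breaks down, so longer wear of Marathon makes its forearm difference negative, whereas greater durability makes the product difference in forearm-minus-elbow positive. The sign has to be set for each endpoint.

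**Conclusion.** The point holds as a gap in estimation. The study is sized on a paired difference against a margin, and no planned table, interval or graph estimates that difference with its uncertainty. At the planning values the missing interval has a half-width of 1.57 A.C.U. at 95% and 1.81 at 97.5%, and it would exclude 15 at the expected difference of 17.5. This part rests only on figures in section 8.1, plus the inference that .0125 is one-sided for the 97.5% level.

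The risk from judging by overlap is real but secondary. Its size depends on a within-person correlation that the documents do not give, and it disappears at the planned difference. What does not depend on the correlation is that by-product bars cannot show whether the difference exceeds 15. Because the remedy is nearly free and lets the trial address its own margin, it should be made.

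**What to change.** 1. In sections 8.6 and 8.8.1, define the within-participant product difference at each visit, for the forearm and for forearm-minus-elbow. State the sign for each endpoint so that the favourable direction is clear.
2. Report its mean with a paired confidence interval. Fix the level after reconciling P < .05 (section 8.8) with .0125 (section 8.1); it is 97.5% two-sided if .0125 is one-sided.
3. State the endpoint, visit and direction to which the 15 A.C.U. of section 8.1 applies. Plot the difference over time with a reference line at 0 and, for that endpoint, at the correctly signed margin.
4. Keep the by-product graphs and label their bars as descriptive.
5. Make the change together with replacing the independent-sample test by a paired one.

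The cost is some wording and a few lines of analysis code. No new data, visits or participants are needed.
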